### **NNS Assessment and Automated NNS Digital Signal Processing and Feature Extraction**

In addition to the oral stimulation interventions (PULSED NTrainer vs. SHAM pacifier), all study infants will be assessed 3 times/week (e.g., Mon/Wed/Fri) for NNS performance. The NTrainer System® will be used in 'assessment mode' to record the compression dynamics of NNS during a 3-minute session to immediately precede a tube feeding that is not associated with an intervention condition.

The most active 2-minute period of NNS behavior based on suck cycle count is automatically extracted from each suck assessment data file using an automated waveform feature extraction algorithm on the NTrainer System®. The NNS pressure waveform is band-pass filtered (0.5-20 Hz) to remove low frequency offsets due to tongue/jaw posturing and thermal drift associated with oral contact on the pacifier bulb, and to remove high-frequency jitter. Pressure peaks > 1.6 cm H2O are subjected to feature extraction criteria, including suck cycle symmetry, cycle duration, and burst identification defined as two or more NNS events occurring within 1200 ms.

This algorithm permits objective identification of NNS burst activity distinct from non-NNS mouthing compressions or tongue thrusts against the pacifier. Four measures will be objectively extracted from the indexed records of suck compression, including (1) NNS Bursts/min where an individual burst includes 2 or more suck cycles, (2) NNS Cycles/min, (3) NNS Spatiotemporal Index, and (4) NNS compression pressure (cm H2O).

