A-priori power calculation indicated that a sample size of 110 was required for 80% power, with an assumed correlation of 0.60 among repeated measures and a small effect over time (Cohen's $f = 0.10$). This effect was considerably smaller than those observed in our previous empirical data ($f = 0.22-0.24$), suggesting adequate power for the final sample of 114 neonates in this study.

Linear mixed modeling (LMM) analysis was performed for non-nutritive suck (NNS) variables including NNS Bursts/minute, NNS Suck Cycles/minute, NNS Amplitude, NNS Spatiotemporal Index, and the transition to independent oral feeds based on daily measures of percent oral intake (%PO) to examine the effects of GA, PMA, sex (male, female), respiratory diagnosis (non-BPD, BPD), treatment (NTrainer, Sham), intervention phase (0, baseline), (1, low-dose), (2, high-dose), (3, post intervention), and potential interactions. The models

accounted for nesting of repeated measurements within infants (i.e., intraclass correlation), and a proper error covariance structure was determined based on model fit (i.e., adjusted Akaike Information Criterion, Bayesian Information Criterion). In addition, locally estimated scatterplot smoothing (LOESS) analysis was conducted to estimate the trajectory of %PO growth over PMA. All statistical analyses were conducted using R [1] and SAS 9.4 [2].

References

1. R Core Team. R: A language and environment for statistical computing. R Foundation for Statistical Computing (2019) <http://www.R-project.org/>
2. SAS Institute. SAS/STAT 9.4 user's guide. (2002-2012).

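### The %PO model does not adjust for baseline non-nutritive suck, so the arm comparison of oral feeding may be less precise than the collected data allow

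*SAP*

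**What the plan says.** The SAP, under Secondary Outcomes, lists five mixed-model outcomes: four NNS measures and "the transition to independent oral feeds based on daily measures of percent oral intake (%PO". The same explanatory terms are given for all five: GA, PMA, sex, respiratory diagnosis (BPD or not), treatment, intervention phase, and potential interactions. Phase is coded from "intervention phase (0, baseline), (1, low-dose" up to high-dose and post-intervention. NNS appears only as a set of outcomes. The SAP does not say which term or interaction is the arm comparison for %PO.

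The protocol section on NNS assessment states that "all study infants will be assessed 3 times/week (e.g., Mon/Wed/Fri) for NNS performance". With the phase-0 code, this suggests that pre-treatment NNS values exist in both arms. The protocol does not explicitly schedule an NNS recording before the first intervention session; it does so only for saliva.

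The power statement says that "a sample size of 110 was required for 80% power". That figure takes measurements on the same infant to correlate at 0.60 and uses an f of 0.10 for change over time, not for a difference between arms. The number of infants analysed is given as "the final sample of 114 neonates in this study".

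**The concern.** Stimulation starts at 30 weeks' PCA and is given during tube feeds. At that age %PO is probably at or near zero for almost every infant. This is an inference, since the documents give no baseline %PO. If it is right, the outcome's own baseline says little about how an infant will progress. NNS at phase 0 is the obvious substitute: it is measured in all infants and bears on the skill that the intervention targets.

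If baseline sucking predicts later feeding beyond GA, PMA, sex and BPD, leaving it out keeps explainable between-infant variation in the error of the treatment effect. The protocol describes randomisation by software-generated integers and mentions no stratification, so nothing stated in the design balances baseline skill between arms. At stake is the width of the confidence interval for the arm difference in oral feeding, not its validity.

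**Working it through.** **Inputs.** From the SAP: N = 110 required, 114 analysed, 80% power, f = 0.10, correlation 0.60. Assumed, because not stated: 57 infants per arm, two-sided alpha 0.05, four repeated measures (the four phases), sphericity, and the 0.60 reused as the intraclass correlation for %PO. The value of r is not in the documents, so a range is shown.

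**1. The plan's own figure.** For a repeated-measures F test, the noncentrality is λ = f²·N·m/(1 − ρ). With m = 4 and N = 110, λ = 0.01 × 110 × 4 / 0.40 = 11.0 on 3 and (110 − 2) × 3 = 324 degrees of freedom. Power is 79.9%, and 80% needs N = 111 (112 for equal arms). The stated 110 is therefore reproduced for a test over time (or arm by time) with no covariate. It is not power for an average difference between arms. For that, λ = f²·N·m/(1 + (m − 1)ρ) = 0.01 × 114 × 4 / 2.8 = 1.63, and power is about 24%.

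**2. Contrast averaged over time.** Let r be the partial correlation of baseline NNS with an infant's mean %PO, given GA, PMA, sex and BPD. The variance of the arm difference is multiplied by 1 − r², and the equivalent sample size is 114/(1 − r²). For illustration, take an effect that has 80% power unadjusted: (1.96 + 0.84) × √(2/57) = 0.525 SD. Adjusted power is then Φ(2.80/√(1 − r²) − 1.96).

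| r | Variance reduction | SE ratio | Equivalent N | Illustrative power |
|---|---|---|---|---|
| 0.1 | 1% | 0.995 | 115 | 80.4% |
| 0.2 | 4% | 0.980 | 119 | 81.6% |
| 0.3 | 9% | 0.954 | 125 | 83.6% |
| 0.4 | 16% | 0.917 | 136 | 86.4% |
| 0.5 | 25% | 0.866 | 152 | 89.9% |

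If r refers instead to the infant's underlying level (the random intercept), within-infant noise remains in the mean and the gain is a little smaller. The variance factor is (0.6(1 − r²) + 0.4/4)/0.7, giving SE ratios of 0.983, 0.961 and 0.886 at r = 0.2, 0.3 and 0.5.

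**3. Contrast over time.** Take the arm difference in the change from phase 0 to phase 3, in a random-intercept model with intraclass correlation 0.60. Its SE is √(2 × 0.40 × 2/57) = 0.1675, in SD units. Baseline NNS as a main effect leaves it at 0.1675 for every r tried (0 to 0.5), because the infant-level term cancels in the change.

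If phase-0 %PO is close to zero for nearly all infants, however, the change is essentially the phase-3 value, and the contrast becomes a between-infant difference at phase 3. Baseline NNS interacted with phase can then remove r² of that variance, with r now the correlation with phase-3 %PO. This last step is reasoning from the near-zero assumption, not a computed result.

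**4. Chance imbalance.** With 57 per arm, the baseline difference between arms has SD √(2/57) = 0.19 in standardised units, so a difference of at least 0.2 SD arises in about 29% of such trials. At r = 0.3, an imbalance of 0.2 SD shifts the average %PO difference by 0.3 × 0.2 = 0.06 SD. This is the same variance as in step 2 seen in a single trial, not a further cost.

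**The case against.** The case for leaving the model alone is substantial. It already contains GA, PMA, sex and BPD, which may carry most of what baseline sucking would predict. NNS at about 30 weeks may itself be near floor, and a single 3-minute recording is noisy. The documents do not say how many infants have a recording before the first session. The section title and the smoothing analysis both concern growth in %PO, so the natural arm effect may be treatment by phase or by PMA, for which a main-effect covariate gains nothing. The SAP also reports completed work, so a covariate chosen now, from four NNS measures, is post hoc.

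Most of this stands, and it limits the claim. The gain is unknown and could be close to zero, the covariate needs a time interaction if the contrast is over time, and the result must be labelled as added later. It does not remove the point, because the data appear to be in hand and the cost is very small.

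A reader might infer three stronger things that the documents do not support:

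- That the %PO comparison is biased. Under randomisation, omitting a baseline covariate costs efficiency only.
- That precision has certainly been lost. This needs a value of r, and none is given.
- That the trial's power would rise from 80% to 90%. The stated 80% is for an effect over time, and the 90% needs r = 0.5, for which the documents offer no evidence.

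**Conclusion.** The point holds as a modest opportunity to improve precision. Baseline NNS is absent from the %PO model, and the trial appears to hold it for both arms. For an average arm difference, adjustment would cut the variance by r²: negligible up to r = 0.2, and material from about 0.3 to 0.4. For an arm difference over time, it helps only through an interaction with phase or PMA. Validity and the stated sample size are unaffected.

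The figures assume 57 infants per arm, two-sided alpha 0.05, four phases, an intraclass correlation of 0.60 borrowed from the power statement, and phase-0 %PO near zero where the interaction argument is used. The gap that is certain, whatever r is, is that the SAP does not name the %PO treatment contrast.

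**What to change.** In the SAP's Secondary Outcomes section:

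1. Name the %PO treatment contrast: main effect, treatment by phase, or treatment by PMA.
2. Add an adjusted %PO model that includes each infant's mean phase-0 NNS cycles/min, using only recordings made before the first session. Include its interaction with phase or PMA when the contrast is over time.
3. For an infant with no phase-0 recording, use the overall baseline mean with a missing indicator, so that no randomised infant is dropped. Report how many infants this affects in each arm.
4. Label the model as added after the original analysis and report it beside the existing one, whatever it shows.

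The cost is a few sentences, one re-run and a few degrees of freedom: one for the covariate, one for the indicator, and three more if the covariate interacts with the four phases. No new data are needed.

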## Protocol

Preterm infants will be recruited at gestational age 240/7-286/7 weeks GA. Each infant will be randomized to receive either the PULSED NTrainer or SHAM intervention using a software random integer function in Minitab v.17 (www.minitab.com). As shown in Figure 1, infants assigned to the PULSED NTrainer group will receive a progressive dose of the pulsatile orocutaneous stimulation. Beginning at 30 weeks' PCA, these infants will receive 2 weeks of low-dose PULSED NTrainer stimulation (2 x 3-minute blocks) with a 1-minute stimulus 'off-period' between the stimulation blocks. This form of stimulation will be given simultaneous with tube feedings 3 times/day. The stimulus dose will then be increased over the next 2 weeks (3 x 3-minute blocks of PULSED NTrainer stimulation) with a 1-minute stimulus 'off-period' between the stimulation blocks, also given simultaneously with tube feedings 3 times/day. Preterm infants randomized to the SHAM condition will be given a regular silicone pacifier during tube feedings over the same time period.

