### **PO Feeding Advancement**

Preterm infants will advance on a standardized cue-based feeding schedule utilized by each site NICU, known as Infant Driven Feeding® that will lead to full nipple feeds. This standardization of oral feeding advancements across sites will limit confounders that may ultimately skew the data.

Preterm infant participant data will be managed with our Neonatal Oromotor Database, a custom software developed in the [name] laboratory specifically for NTrainer studies in the NICU. This database software is compatible with MS WIN operating systems, and is password-protected and coded as an executable for MS ACCESS 2013. This software provides a paperless, efficient system for NICU study personnel to log daily information including GA, growth parameters, medications, oxygen requirement, feeding history, medical procedure log, comments, as well as NTrainer/SHAM and salivary sampling dates on enrolled infants.

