### **Saliva Collection, Processing, and Gene Expression Analysis**

*Saliva Collection:* Saliva samples will be collected from all enrolled infants on the first day prior to receiving either the SHAM or PULSED NTrainer intervention. This sample will serve as our baseline gene expression profile. Samples will then be obtained twice per week (~3 day intervals) up to the time of achievement of full oral feeds or discharge home from the hospital with either a nasogastric tube (NG) or gastrostomy tube.

Saliva samples at each site will be collected with techniques that have been optimized and validated through the [name] laboratory. Briefly, saliva samples will be collected with a 1 mL syringe, end caps removed and attached to low wall suction. Saliva will be collected for approximately 20 seconds and immediately stabilized in 500 µL of Qiagen's RNA Protect Saliva to halt gene expression changes, inhibit destructive RNases, and limit microbial overgrowth. Samples will be vortexed briefly and frozen at -20°C. Once frozen, samples are stable for up to 18 months prior to the need for total RNA extraction. Thus, samples from Nebraska and Santa Clara will be shipped once a month on ice overnight to the [name] laboratory at the Mother Infant Research Institute at Tufts Medical Center in Boston, MA for processing.

*Generation of a Saliva Biobank:* One additional saliva sample will be obtained each week from all enrolled subjects to generate a biobank repository. The rationale for this approach is twofold. First, it is possible that during shipment or processing, salivary RNA may be destroyed and not be of sufficient quality to incorporate into the study. Prior studies from this lab have demonstrated a 10% failure rate of gene amplification in saliva samples. Banking an additional sample each week from study subjects will ensure that we will limit loss of data points. Second, we anticipate that there are informative salivary biomarkers of oral feeding maturation that have yet to be identified. By generating a biobank of additional saliva samples that may be retrospectively interrogated on either a microarray gene expression platform or with RNASeq, we will have the potential to discover novel hypotheses about gene-gene interactions and/or transcriptional regulatory processes related to oral feeding in the preterm population.

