Official Title: Somatosensory Modulation of Salivary Gene Expression and Oral Feeding in Preterm Infants

NCT number: NCT02696343

Document Date: 3-31-24

Statistical Analysis Plan.

Primary Outcome: Gene Expression

In this randomized controlled clinical trial, we analyzed salivary developmental gene expression changes in extreme and very preterm infants randomized to receive either therapy with the NTrainer feeding system or a 'Sham' mode (blind pacifier) to assess the effect of therapy on the developing infant. Salivary samples were collected at a series of timepoints, beginning with the initiation of therapy through the learning process of oral feeding or to transfer to an outlying hospital. The primary goal of this study was to assess and compare differences in gene expression patterns over time between groups. The expression of six genes involved in 1.) memory: *CDH13*; oral development: *FOXP2* and *WNT3*; 3.) sensory integration: *NPHP4*, and *PLXAN1*; and hunger signaling: *NPY2R*, along with two reference genes for proper normalization were measured via RT-qPCR for each subject at 6 timepoints. The raw CT values were normalized for each subject and timepoint by subtracting the geometric mean of the reference genes from the mean expression of each gene (deltaCT). These deltaCT values were used for the remainder of the analysis. A positive deltaCT value indicates that the target gene had lower expression than the reference gene; conversely increasing deltaCTs are indicative of decreasing expression. In order to determine changes in gene expression, one way and two-way ANOVA analysis in R [1] was used. Initially, the analysis was done to assess expression pattern changes over time for 1.) the cohort as a whole, 2.) based on treatment status, and 3.) by sex. Given that the timepoint measurements are done on the same subject, repeated measure ANOVA and subject for which all time points were not measured were excluded from the analysis. Subsequently, the analysis was extended by grouping subjects by bronchopulmonary dysplasia (BPD) status, looking at the effect over time, the effect of treatment status and the interaction of the two. BPD was defined based on NIH criteria.

Secondary Outcomes: Non-nutritive Suck Dynamics and Growth in Daily Oral Feeds

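### No listed model includes site, although the trial is multi-site and no site stratification is described: a minor, cheaply recovered loss of precision in the treatment main effects

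*SAP*

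**What the plan says.** **Sites.** The protocol refers to more than one NICU in PO Feeding Advancement ("standardized cue-based feeding schedule utilized by each site NICU"), in Neurodevelopmental Follow-Up, and in the saliva section, where "samples from Nebraska and Santa Clara will be shipped once a month on ice overnight" to the Boston laboratory. Two sites are named. Boston's own enrolment is an inference, and neither the number of sites nor the infants per site is given.

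**Allocation.** Under the heading Protocol: "Each infant will be randomized to receive either the PULSED NTrainer or SHAM intervention", "using a software random integer function in Minitab v.17". No blocks, strata or site factor are mentioned, and no allocation ratio is stated.

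**Primary analysis (SAP, Primary Outcome).** The stated goal is to "assess and compare differences in gene expression patterns over time between groups". The ANOVAs look at change over time for "1.) the cohort as a whole, 2.) based on treatment status, and 3.) by sex". A later extension groups infants by BPD status and examines time, treatment status and their interaction.

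**Secondary analysis (SAP, Secondary Outcomes).** The mixed models are fitted "to examine the effects of GA, PMA, sex (male, female), respiratory diagnosis (non-BPD, BPD), treatment (NTrainer, Sham", plus intervention phase and possible interactions. They "accounted for nesting of repeated measurements within infants (i.e., intraclass correlation" but have no level or term for site.

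**The concern.** Site balance is protected neither by the allocation as described nor by the analysis. The outcomes could plausibly differ by site. Cue-based feeding depends on readiness judged at the bedside, and percent oral intake is a modelled outcome. Saliva from two sites travels to the laboratory, and the protocol itself allows that RNA can be lost in shipment or processing. If site means differ, that variation sits in the error term of any treatment main effect, and whatever arm-by-site imbalance arose by chance stays in the estimate. Site is known for every infant, so the loss is avoidable.

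**Working it through.** **1. The plan's own figure.** The SAP gives 110 infants for 80% power, with f = 0.10 and correlation 0.60. It does not give the number of repeated measures m or alpha. Assume m = 4 (the four intervention phases), alpha 0.05 and sphericity. Then λ = f²·N·m/(1 − ρ) = 0.01 × 110 × 4 / 0.40 = 11.0, with 3 and 324 df, and power is 0.799. The smallest N reaching 80% is 111, so the figure reproduces under this assumption. Other values of m give 159 (m = 2), 130 (3), 97 (5) and 87 (6). The calculation concerns an effect over time within infants, so it does not size the treatment main effects discussed here.

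**2. Loss for a treatment main effect.** Let v be the share of variance in the infant-level quantity that site explains beyond the covariates already in the model. The documents give no v, so a range is assumed. Variance inflation from omitting site is 1/(1 − v) − 1. The 114 infants are then worth 114 × (1 − v) under a site-adjusted analysis. A contrast with 80% power unadjusted would have power Φ[(1.96 + 0.84)/√(1 − v) − 1.96] with site included.

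| v (assumed) | Variance inflation | 114 infants worth | 80% power becomes |
|---|---|---|---|
| 0.02 | 2% | 112 | 81% |
| 0.05 | 5% | 108 | 82% |
| 0.10 | 11% | 103 | 84% |
| 0.20 | 25% | 91 | 88% |

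These figures ignore the small cost of the site terms. Simulation with that cost included (three equally likely sites, 1:1 allocation, m = 4, correlation 0.60) gives an unadjusted-to-adjusted SE ratio of 1.04 at v = 0.10 and 1.11 at v = 0.20.

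**3. Chance imbalance.** With 114 infants, three equal sites and simple 1:1 randomisation (all assumed except 114), the largest between-arm difference in any site's share is at least 10 points in 50% of allocations, 15 points in 21% and 20 points in 6%. For a 50/30/20 split of infants the figures are 46%, 18% and 5%. To illustrate, suppose 15 points move between two sites whose means differ by 0.5 SD. The arm difference then shifts by 0.15 × 0.5 = 0.075 SD, against an ordinary standard error of 2/√114 = 0.187 SD. Averaged over allocations, this is the same loss as in step 2, not an additional one.

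**4. Validity.** The simulated type I error of the unadjusted test is 5.0% for v = 0.05, 0.10 and 0.20.

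**5. The arm-by-time contrast.** Write an infant's value as site shift + infant effect + arm and time terms. A site shift that is the same at every timepoint drops out of any within-infant difference. In simulation, a constant shift holding 10% or 20% of the variance of infant means gives an SE ratio of 0.99 for arm-by-time, so adjustment gains nothing. If instead sites differ in trajectory, and this holds 10% or 20% of the variance of infant slopes, the ratio is 1.05 or 1.11. Recovering that loss needs a site-by-time term; a site main effect alone would not do it.

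**The case against.** The strongest reply is that the design already limits site differences. Every NICU uses the same cue-based feeding programme, and the protocol says this is meant to limit confounding. Saliva is collected by a common validated technique and stabilised at once. Frozen samples are described as stable for up to 18 months, against monthly shipping. Processing takes place in one laboratory, and expression is normalised to reference genes. Suck features are extracted by an automated algorithm. GA, PMA, sex and BPD are in the mixed models and may absorb some case-mix differences. This largely stands: it argues for small v, though limiting a source of variation does not show that it is absent.

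A second reply is that randomisation was not stratified by site, as far as described, so an unadjusted analysis is legitimate and adjustment is a choice about precision. That also stands.

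A reader might go further than the documents allow in three ways:

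- **Bias or false positives.** Simple randomisation gives neither on average; step 4 shows type I error unchanged.
- **A large loss of sample size.** Site means spaced 0.5 SD apart would make adjustment worth about 17% more infants (114/(1 − 0.143) = 133). That spacing is pure assumption, implies that site holds 14% of variance, and concerns main effects only.
- **Damage to the primary comparison from shipping.** A constant handling effect on deltaCT cancels in arm-by-time. The primary analysis also drops infants with any missing timepoint, so 114 need not be its sample size.

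**Conclusion.** The omission is real and the consequence is minor. Site appears in no listed model of a multi-site trial with no site stratification described. The cost falls on the treatment main effects in the suck and percent-oral-intake mixed models and in the BPD extension of the deltaCT analysis. It is a variance inflation of about 2% to 25% over an assumed site share of 2% to 20%, with the lower part more plausible given the standardisation. Comparisons over time, including the primary one, are affected only if sites differ in trajectory; this is most plausible for growth in percent oral intake. The calculations assume three sites, 1:1 allocation, alpha 0.05, four measures and equal correlation between them. The documents supply neither site sizes nor site variance, so no single corrected figure can be given.

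**What to change.** - Report the number of infants by arm and site.
- Add site as a fixed effect to the suck and percent-oral-intake mixed models, and to the deltaCT models that test a treatment main effect. A fixed effect suits so few sites.
- As a sensitivity analysis for over-time comparisons, add site-by-phase or site-by-PMA to the mixed models and site-by-time to the deltaCT models.
- The SAP is written as already performed, so label the site-adjusted results post hoc and show them beside the unadjusted ones.

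The cost with three sites is 2 degrees of freedom for the main term. The interaction adds 2 × 3 = 6 with four phases, 2 with linear PMA, or 2 × 5 = 10 with six timepoints. No new data are needed. If site proves negligible, the estimates will barely move and the reader can see that.

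### No secondary mixed model without BPD is described, and the plan does not show that BPD status was settled before therapy began

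*SAP*

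**What the plan says.** In the SAP's Secondary Outcomes section, one list of effects serves all the mixed models. Besides GA, PMA and sex it contains the two-level factor "respiratory diagnosis (non-BPD, BPD", next to treatment, the four intervention phases and possible interactions. The outcomes are NNS bursts per minute, suck cycles per minute, amplitude, spatiotemporal index and %PO, five in all. No model that leaves BPD out is described.

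In the Primary Outcome section the order differs. The first step does not use BPD: "Initially, the analysis was done to assess expression pattern changes over time for 1.) the cohort as a whole, 2.) based on treatment status", and then by sex. Only afterwards does BPD enter: "Subsequently, the analysis was extended by grouping subjects by bronchopulmonary dysplasia (BPD) status, looking at the effect over time, the effect of treatment status", together with the interaction.

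On what BPD means, the SAP says only that "BPD was defined based on NIH criteria". It gives no age or date of classification. Neither document calls BPD a baseline or stratification variable. The randomisation described in the Protocol section is a random integer function, with no mention of respiratory status.

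On timing, the Protocol section recruits infants at 24 0/7 to 28 6/7 weeks GA and starts therapy later: "Beginning at 30 weeks' PCA, these infants will receive 2 weeks of low-dose PULSED NTrainer stimulation", followed by two weeks at the higher dose. The date of randomisation is not given.

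**The concern.** Randomisation makes the arms comparable on everything fixed before treatment. It gives no such protection for a diagnosis reached during or after treatment. If treatment can change that diagnosis, conditioning on it causes two problems. Any part of the effect that runs through BPD is removed from the estimate. In addition, within each BPD group the arms are no longer alike, because infants reached that group partly through their course on treatment.

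For the five secondary outcomes the described models offer no unconditioned estimate to set beside the adjusted one. For both the secondary models and the gene extension, a reader cannot tell whether results by BPD are effects in a baseline subgroup or in groups formed after randomisation. Under a late label, the mixed models would also use a later diagnosis to explain measurements from the baseline phase.

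**Working it through.** The plan states no figure on this point, and the fix changes no stated sample size or power. The check has three parts.

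**1. When could the label fall relative to therapy?**

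Inputs from the Protocol section: GA 24 0/7 to 28 6/7 weeks (read as GA at birth), therapy from 30 weeks' PCA, and 2 + 2 = 4 weeks of therapy, so a planned end at 34 weeks. The documents give no classification age. Two are assumed here to show the range.

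- Label at 28 days of age (4 weeks): 24 0/7 + 4 = 28 0/7 weeks and 28 6/7 + 4 = 32 6/7 weeks' PCA. The label falls on the planned start day when GA at birth is 30 0/7 − 4 = 26 0/7. Infants born beyond 26 0/7 are labelled after the planned start, and those born earlier are labelled before it. Of the 35 eligible GA days, 14 (24 0/7 to 25 6/7) fall before, 1 coincides and 20 (26 1/7 to 28 6/7) fall after. The documents give no GA distribution, so these counts cannot be turned into a share of infants.
- Label at 36 weeks' PCA: 36 − 34 = 2 weeks after the planned end of the course, for every infant who starts on schedule.

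**2. How much bias could conditioning produce when the true effect is nil?**

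This is an illustration with every input assumed: one outcome per infant, 1,000,000 simulated infants, equal allocation and 50% BPD in the sham arm.

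- Severity U is standard normal. BPD liability is L = 0.7U + √(1 − 0.49) × noise, and BPD is present when L exceeds a threshold.
- The outcome is Y = −bU + noise, scaled to SD 1, with no treatment effect on Y.
- Treatment moves the threshold so that BPD risk falls by 0, 5, 10 or 20 points.
- The adjusted difference is the treatment coefficient from a linear regression of Y on treatment and BPD.

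| Fall in BPD risk | Adjusted, b = 0.5 | Adjusted, b = 1.0 |
|---|---|---|
| 0 points | −0.001 SD | −0.003 SD |
| 5 points | −0.027 SD | −0.042 SD |
| 10 points | −0.050 SD | −0.082 SD |
| 20 points | −0.103 SD | −0.162 SD |

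The unadjusted difference is −0.002 or −0.003 SD throughout, which is zero within simulation error. The contrasts within BPD groups show the same bias. At a 10-point fall they are −0.049 (no BPD) and −0.052 (BPD) for b = 0.5, and −0.079 and −0.085 for b = 1.0.

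**3. How much of a real effect could be adjusted away?**

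Removed effect = shift in BPD risk × effect of BPD on %PO. Assume a shift of 5 to 10 points and a 20-point lower %PO with BPD: 0.05 × 20 = 1 and 0.10 × 20 = 2 %PO points.

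Parts 2 and 3 are separate mechanisms. Neither takes an effect size from the documents.

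**The case against.** A reader might infer that BPD was certainly decided after randomisation and that the models therefore break the randomised comparison. The documents do not support that, for four reasons.

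- **Timing is not stated.** The SAP cites NIH criteria without an assessment age, and no randomisation date is given. Under the 28-day assumption, infants born before 26 0/7 weeks would be labelled before the planned start, so treatment could not have affected their label. The criteria for starting in the Orocutaneous Stimulation Regimen section could also delay therapy. That would put more 28-day labels before it, and a delay beyond 2 weeks would move the end of the course past 36 weeks.
- **A late label is not enough.** The zero row of the table shows no bias when treatment leaves BPD risk unchanged. Nothing in the documents says that the stimulus affects BPD, and BPD is not among the listed outcomes.
- **The first primary comparison is untouched.** It is made by treatment before BPD is introduced.
- **The sizes are assumed, and modest.** The SAP also never calls its BPD results baseline subgroup effects.

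All of this stands, and it limits the point to the secondary mixed models and the BPD extension. It does not remove the point. The documents do not show BPD to be a baseline variable, they give no ground for ruling out an effect of treatment on it, and they describe no secondary model from which a reader could see whether the adjustment matters.

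**Conclusion.** The point holds conditionally. The firm part is an omission: for five secondary outcomes no treatment estimate free of BPD is described, and for those models and the gene extension the timing of BPD is unstated. Bias then requires two further conditions: classification after therapy began, and an effect of treatment on BPD. If both hold, the illustrations suggest a distortion of about 0.03 to 0.08 SD, or 1 to 2 %PO points, for a 5 to 10 point shift in BPD risk. A 20-point shift gives about 0.10 to 0.16 SD. If treatment does not affect BPD, the factor is simply prognostic. The primary treatment comparison is not in question. The change is worth making because it protects the randomised comparison whenever BPD was classified, and it is cheap.

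**What to change.** For each of the five secondary outcomes, report as the main estimate the treatment effect from a mixed model without BPD. Keep GA, which is already in the model. If respiratory adjustment is wanted, use oxygen requirement on the day therapy starts, recorded before the first session. The daily log in the PO Feeding Advancement section lists "medications, oxygen requirement, feeding history". That list does not name respiratory support, so the plan should not rely on it for that.

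State in the SAP the age at which BPD was classified. Keep the BPD-adjusted mixed models and the BPD-grouped gene analyses, but label them exploratory and note that they may condition on a diagnosis made after randomisation.

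The cost is one more fit per secondary outcome and a few sentences. The SAP reports completed analyses, so no new data collection is involved. The downside is a possible small loss of precision if BPD explains more outcome variance than GA and oxygen requirement at the start do.
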